#### 7.1.2. Thiopurine Methyltransferase Testing

A thiopurine methyltransferase (TPMT) phenotyping test will be performed to confirm if the subject is eligible.

Subjects must consent to having this test done. The test will be performed at:

Black County Pathology Services

[name], Royal Wolverhampton Hospitals NHS Trust,

[name]

The results of the test will be discussed appropriately with the subject.

#### 7.1.3 Schedule of Study Assessments:

The timing of assessments is displayed in Table 7-1.

The time of dosing commencement may vary for logistical reasons. Actual clock times will vary between subjects, in relation to actual dosing times.

Assessment	Screening*	Admission 1 Day -1**	Treatment period 1	Admission 2 Day -1**	Treatment period 2***	Post- study Visit 
Informed consent	Х					
Demographic and anthropometric data 	Х					
Alcohol and tobacco consumption and drug use	X					
Medical history  and prior medication	Х	Х				
Adverse events and concomitant medication		X \$	Х	Х	Х	Х
Physical examination 	Х					Х
Vital signs 	Х		Х		Х	Х
12-Lead ECG 	Х					Х
Haematology 	Х	Х		Х		Х
Clinical chemistry 	Х	Х		Х		Х
Blood coagulation 	Х	Х		Х		Х
Serology tests 	Х					
Urinalysis 	Х					
Urine screen for drugs of abuse 	Х	Х		Х		
Urine screen for tobacco use 	Х	Х		Х		
Pregnancy Test 	Х	Х		Х		Х
Eligibility Assessment	Х	Х		Х		
Randomization			Х			
IMP administration			Х		Х	
PK profile 			Х		Х	
Palatability questionnaire 			Х		Х	
Alcohol breath test 	Х	Х		Х		
Study specific screening test 	Х					

#### Table 7-1Schedule of Study Assessments

IMP = investigational medicinal product; ECG = electrocardiogram; PK = pharmacokinetic

\* Screening procedures can be performed over more than one visit

\*\* Day -1 Safety Labs can be performed within 7 days of dosing. If screening is performed within 7 days of dosing (for treatment period 1 only) safety labs do not need to be repeated. Subject will return to the unit in the afternoon/ evening of Day -1 for admission and remaining admission tests.

\*\*\*Treatment Period 2 to be carried out 3 to 14 days days of Treatment Period 1.

§ Concomitant Medications only at admission, as only treatment emergent adverse events will be recorded.

1. Seven (7) to ten (10) days after the last dose of the last period of the study or, in the case of discontinuers or drop-outs who took the IMP, within 72 hours of withdrawal/withdrawing from the study.

2. Gender, race, date of birth, age, height, weight and BMI.

3. The recorded medical history will be updated if necessary on pre-profile nights (Day -1 of Admission 1).

4. A full physical examination will include the following: ear/nose/throat, ophthalmological, dermatological, cardiovascular, respiratory, gastrointestinal, central nervous system, lymph nodes and musculoskeletal.; other evaluations may be performed as deemed necessary by the investigator. Any other evaluations undertaken will be included in the clinical study report, if applicable. The post-study physical examination will only be brief but will include vital signs.

5. Supine and standing systolic and diastolic blood pressure, pulse and body temperature (tympanic) at screening (supine vital signs measured following 5 mins rest in supine position, standing vital signs measured following 2 mins in standing position). Supine blood pressure, pulse and body temperature will be recorded before administration of IMP; in addition, supine blood pressure and pulse will be recorded at 2, 4 and 6 hours (+/- 10 mins) post-dose and at post study visit.

6. Standard 12-lead ECG will be performed at screening and post-study following 5 mins rest in supine position.

7. Haematology (Ethylenediaminetetraacetic acid [EDTA tubes]): leucocytes, erythrocytes, haemoglobin, hematocrit, platelets, basophils, monocytes, neutrophils, eosinophils and lymphocytes (absolute count and percentages).

8. Screening and post-study: Clinical chemistry (Serum separator tubes [SST]): potassium, sodium, urea, creatinine, uric acid, calcium, protein, albumin, total bilirubin, alkaline phosphatase (ALP), gamma glutamyl transferase (GGT), aspartate

aminotransferase (AST), alanine aminotransferase (ALT) and glucose. The clinical chemistry performed during admission of treatment periods 1, 2 and at post treatment will only include the liver function tests GGT, ALP AST and ALT.

9. Blood coagulation tests (citrated tubes): Prothrombin time (PT), activated partial thromboplastin time (aPTT) and International Normalised Ratio (INR).

10. Tests for human immunodeficiency virus (HIV) and Hepatitis B and C, performed. Pre- and post-test counselling will be provided as appropriate.

11. Urinalysis (dipstick): protein, bilirubin, blood and urobilinogen.

12. Using a single urine sample: amphetamines, cannabinoids, cocaine, barbiturates, benzodiazepines, opiates, methadone.

13. Cotinine testing.

14. Serum pregnancy testing at screening (where applicable). Urine pregnancy testing at admission 1, 2 and Post-Study Visit for women of child bearing potential only.

15. Blood collections will be made pre-dose within 30 minutes before administration and at 15 mins ( $\pm 2$  mins), 30 mins ( $\pm 2$  mins), 45 mins( $\pm 2$  mins), 1hr ( $\pm 2$  mins), 1 hr 20mins( $\pm 2$  mins), 1 hr 40mins ( $\pm 2$  mins), 2hrs( $\pm 5$  mins), 2hrs 20 mins( $\pm 5$  mins), 2hrs 40 mins ( $\pm 5$  mins), 3hrs( $\pm 5$  mins), 4hrs( $\pm 5$  mins), 5hrs( $\pm 5$  mins), 6hrs( $\pm 5$  mins), 8hrs( $\pm 5$  mins) and 12hrs( $\pm 5$  mins)) after study drug administration. The PK sample should be taken on the scheduled timepoint and other procedures due at the same time scheduled around using the applicable windows.

16. A short palatability questionnaire will be completed after dosing on the day that the subject is given oral liquid only. 17. Alcohol breath test using a portable breath alcohol measuring device will be performed at screening, on admission to the research centre of each treatment period and at random, at any time during the study, if deemed necessary by the principal investigator or designee, to detect the presence of alcohol. If any of these tests are positive, subjects will not be allowed further participation in the study.

18. Study-specific screening tests: Thiopurine methyltransferase (TPMT) testing (EDTA tubes) (see Appendix 15.1).

# 7.1.4 Safety and Data Monitoring Committees:

Not applicable.

# 7.2 Discussion of Study Design

Bias is prevented by strict adherence to the inclusion and exclusion criteria. All measurements and procedures are clearly defined in advance and will consistently and precisely be applied.

# 7.2.1 Pre-study Evaluation (Screening)

Within 28 days prior to the first administration of IMP and after written informed consent is obtained, screening procedures will be performed on each subject (see Table 7-1). Subjects who meet the inclusion criteria (Section 7.3.1) will be considered eligible to participate in the study. Subjects who meet one or more of the exclusion criteria (Section 7.3.2) will not be considered eligible to participate in the study. The total screening period will be approximately 28 days.

At the discretion of the investigator screening procedures may be repeated

# 7.2.2 Expected Duration of Study

The duration of this study is expected to be approximately 2 months per subject (excluding the screening period). The actual overall study duration or subject recruitment may vary.

# 7.2.3 Treatment Periods (1 and 2)

Each treatment period will include a PK profile period of 12 hours, which will commence with morning dosing of IMP on a 12-hour clinic stay at the study centre.

During all treatment periods subjects will have safety laboratory tests performed within 7 days prior to dosing (if screening is performed within 7 days of dosing (for treatment period 1 only), safety labs do not need to be repeated). They will be admitted to the study centre on the afternoon/ evening of Day -1 for remaining admission tests. An overnight fast of at least 10 hours (a food and beverage-free period with the exception of water) will be observed.

Before dosing on day 1, an indwelling venous cannula may be inserted. A member of the clinical team will decide when to remove or replace the venous cannula based on the time (since insertion of the cannula) or if clotting occurs. If the cannula is removed, the subsequent blood samples will be collected by venepuncture or the cannula will be replaced.

The IMP will be administered in the sitting position with the volume of water specified in section 8.6. Thereafter subjects will be required to refrain from lying down (except when required for clinical procedures e.g. PK sampling) for 4 hours after dosing.

Food and beverages on clinic days will be according to Section 7.2.7.1.

A short palatability questionnaire will be given to the subjects on the day that oral liquid is given and will comprise:

- 1. What did you think of the taste of the liquid medicine you were given in the study?
- 2. Was there an aftertaste to the liquid medicine you were given in the study?
- 3. What did you think of the smell of the liquid medicine you were given in the study?
- 4. What did you think of the texture of the liquid medicine in the mouth?
- 5. If you had to, how easy would it be for you to take the liquid medicine regularly, every day?

Subjects will be allowed to leave the study centre on the treatment days after the last assessments have been made.

#### 7.2.4 Post-study Evaluations

See Table 7-1.

If a subject is withdrawn or chooses to withdraw from the study, the investigator will make every effort to perform all evaluations described for the post-study visit.

Post study laboratory investigations with variables outside the reference ranges will not necessarily be repeated to establish if and when those variables returned to within the reference ranges. The variables will be reviewed against the clinical background, other relevant investigations and their relevance to the administered IMP, before a decision will be taken to repeat the investigations in question. At the discretion of the investigator, the investigations of certain variables outside the reference ranges may be repeated until the variables return to within the reference range for the particular laboratory test, or until the investigator considers the repeated variable to be at an acceptable level in relation to the reference range. If the investigator has made every effort to contact the subject and the subject remains unavailable to attend the clinic for repeat of applicable laboratory investigations, the investigator may declare the subject lost to follow-up.

In cases where results of post-study evaluations are reported after the database has been locked, the applicable clinical laboratory reports will be presented in the appendices to the clinical study report.

All evaluations described for the post-study visit will be performed on all subjects who completed the study.

#### 7.2.5 Sampling, Interim Handling and Storage

#### 7.2.5.1 Safety Blood and Urine Samples

Refer to Table 7-1.

Before starting the study, the investigator (or designee) will supply the sponsor with the reference ranges and units of measurement for the laboratory safety variables to be used during the study. If

the reference ranges change during the course of the study, the investigator (or designee) must provide the sponsor with a list of the new reference ranges and the effective dates.

The TPMT deficiency test will be performed by Black County Pathology Services.

All safety blood and urine sampling will be performed by the study centre, according to their local standard operating procedures (SOPs).

The principal investigator or designee will ensure that all biological fluids collected during the study will not be used for purposes other than as directed by the clinical study protocol. All collected biological fluids used for safety investigations will be destroyed within 3 months after the clinical execution of the study has been completed. All biological fluids used for the TPMT deficiency tests performed at Black County Pathology Services will be destroyed there after the clinical execution of the tests required have been completed.

# 7.2.5.2 Pharmacokinetic Blood Samples

Pharmacokinetic blood samples will be collected at the following times: Blood collections will be made pre-dose within 30 minutes before administration and at 15 mins ( $\pm 2$  mins), 30 mins ( $\pm 2$  mins), 45 mins( $\pm 2$  mins), 1hr( $\pm 2$  mins), 1 hr 20mins( $\pm 2$  mins), 1 hr 40mins ( $\pm 2$  mins), 2hrs( $\pm 5$  mins), 2hrs 20 mins( $\pm 5$  mins), 2hrs 40 ( $\pm 5$  mins), 3hrs( $\pm 5$  mins), 4hrs( $\pm 5$  mins), 5hrs( $\pm 5$  mins), 6hrs( $\pm 5$  mins), 8hrs( $\pm 5$  mins), and 12hrs( $\pm 5$  mins) after study drug administration. The total number of blood collections will be 32, 16 samples per period. The total volume of blood taken (including safety bloods) will be approximately 356.3 ml. The actual blood sampling times will be recorded in the eCRFs. The PK sample should be taken on the scheduled timepoint and other procedures due at the same time scheduled around using the applicable windows.

Venous blood samples, up to 10 mL each, for the determination of azathioprine concentrations will be collected. Full details on PK collection, sampling, processing and storage will be provided in a study specific lab manual

Blood samples taken for drug concentration measurements will be analysed by Alderley Analytical according to applicable SOPs.

Unused duplicate plasma PK samples will be stored at Alderley Analytical for up to 1 year after completion of the study (defined as last subject last visit). The sponsor will be required to indicate whether additional storage is needed or whether the samples may be discarded.

# 7.2.6 Blood Volume

The total blood volume to be collected from each subject during the study is indicated in Table 7-2.

The total volume of blood to be collected from each subject during the study (approximately 230 mL) is considered acceptable.

Procedure	Visit	No. Samples	Blood Volume per Sample (mL)	No. Treatment Periods	Blood Volume (mL)	
Clinical	Screening 	1	5	N/A	5	
chemistry	Admission	1	2.5	2	5	
chennsuy	Post-study	1	2.5	N/A	2.5	
E-111.1.1.1	Screening 	1	2	N/A	2	
Full blood	Admission	1	2	2	4	
count	Post-study	1	2	N/A	2	
D1 1	Screening 	1	2.7	N/A	2.7	
Blood	Admission	1	2.7	2	5.4	
coagulation	Post-study	1	2.7	N/A	2.7	
Azathioprine 	Treatment Period	16	~10	2	320	
Study specific screening	Screening	1	5ml (EDTA)	N/A	5	
Total Blood Volume 356.3						
 From the screening biochemistry blood samples, virology screen will be conducted.						

Table 7-2Total Blood Volume to be Collected during the Study

 Note that there will be 1ml waste collected for each post dose timepoint

# 7.2.7 General and Dietary Restrictions

#### 7.2.7.1 Diet

Consumption of grapefruit, grapefruit juice, Seville oranges or orange marmalade, cruciferous vegetables (e.g., cabbage, broccoli, sprouts), liquorice, peppermint-containing products, char-grilled foods, poppy seeds or cranberry juice will not be allowed from 7 days before the start of the study until after completion of the study.

The ingestion of food and beverages containing pineapple and all other fruit juices will not be allowed for 72 hours before the administration of IMP and until the last PK blood sample is collected per treatment period.

The ingestion of food and beverages containing methylxanthines e.g., caffeine (coffee, tea, chocolate, energy drinks and cola) will not be allowed for 72 hours before the administration of IMP and until the last PK blood sample is collected per treatment period. Decaffeinated alternatives are permitted.

The ingestion of food and beverages containing alcohol will not be allowed for 72 hours prior to any safety laboratory samples and for 72 hours before screening and then from 72 hours before the first administration of IMP (treatment period 1) until the last PK blood sample (treatment period 2) is collected.

Food and beverage intake during the clinic stay will be as per clinical unit standard practice

No fluids (apart from water taken with dose) are allowed from 1 h prior to dosing until 1 h afterwards. Water is then allowed ad libitum.

While resident in the clinic, volunteers will follow a standard meal schedule. After a snack on the evening of admission they will be fasted overnight until lunchtime on Study Day 1

Lunch: Approx 4.5 hours post dosing

Snack: Approx 7.5 hours post dosing

Dinner: Approx 10 hours post dosing

Food and beverage intake will be allowed *ad libitum*, unless restrictions apply, after the subjects have been discharged from the clinic.

# 7.2.7.2 Physical Activity

Strenuous physical activity will not be allowed for 72 hours before the first dose of either treatment period until after discharge.

#### 7.2.7.3 Contraception

To prevent pregnancy female subjects of child bearing potential and male subjects and their female partner must use a condom plus 1 highly effective form of contraception i.e.,

- Condom + Established use of combined hormonal contraception associated with inhibition of ovulation:
  - o Oral
  - o Intravaginal
  - o Transdermal
- Condom + Established use of progestogen-only hormonal contraception associated with inhibition of ovulation:
  - o Oral
  - o Injectable
  - Implantable
- Condom + Intrauterine device (IUD).
- Condom + intrauterine hormone-releasing system (IUS).
- Vasectomised partner, provided that partner is the sole sexual partner of the female trial subject and that the vasectomised partner has received medical assessment of the surgical success and this documented evidence is available.
- True abstinence, only if defined as refraining from heterosexual intercourse during the entire period of risk associated with the study treatments and up to 6 months after. The reliability of sexual abstinence needs to be evaluated in relation to the duration of the clinical trial and

the preferred and usual lifestyle of the subject. [Periodic abstinence (e.g., calendar, ovulation, symptothermal, post-ovulation methods) and withdrawal are **not** acceptable methods of contraception].

The chosen contraception method(s) must be followed from the first dose until at least 6 months after the last dose of IMP.

To prevent exposure of any partner (male or female) a condom must be used throughout the study and for 6 months after the final dose of study drug

Male subjects must not have unprotected sexual intercourse with a female who is pregnant or breastfeeding during the study and for 6 months after their final dose.

Contraception advice will be documented in the informed consent form.

#### 7.2.7.4 Sperm and Oocyte Donation

Subjects must not donate sperm or oocytes from the first dose and for at least 6 months after the last dose of IMP.

# 7.2.7.5 Receipt of Live Vaccination

Subjects must not receive live vaccinations 4 weeks prior to first dose and for at least 3 months after the last dose of IMP.

# 7.3 Selection of Study Population

The criteria are set to ensure a homogeneous subject population without accompanying diseases interfering with the conduct and scientific evaluation of the study. Additionally, the criteria have been selected to minimize risk to the subjects' well-being.

#### 7.3.1 Inclusion Criteria

- 1. Healthy male and female subjects, 18 years to 55 years inclusive at time of signing the informed consent document
- 2. Females child Bearing potential with a negative pregnancy test at screening and willing to use a condom plus 1 highly effective method of contraception from first dose until 6 months after last dose of IMP (please see section 7.2.7.3 for contraception details).
- 3. Females of Non child Bearing potential defined as those who have no uterus, ligation of the fallopian tubes, or permanent cessation of ovarian function due to ovarian failure or surgical removal of the ovaries.( A urine pregnancy test will be required for subjects without Medical documentation to support non child bearing status) or Post-menopausal females defined as being at least 45 years of age with history of amenorrhoea for 12 months without an

alternative medical reason. A confirmatory follicle-stimulating hormone (FSH) may be performed at the discretion of the site Investigator to confirm postmenopausal status.

- 4. Male subject willing to use 2 highly effective methods of contraception from first dose until 6 months after last dose of IMP (please see section 7.2.7.3 for contraception details).
- 5. Body Mass Index (BMI) between 18 and 33 kg/m^2.
- 6. Body weight not less than 50 kg.
- 7. Subject with no clinically significant abnormal serum biochemistry, haematology and urine examination values within 28 days before the first dose of IMP.
- 8. Medical history, physical examination, standard 12-lead electrocardiogram (ECG) and vital signs investigations: Findings clinically acceptable or within reference ranges, unless the investigator considers the deviation to be irrelevant for the purpose of the study.
- 9. Non-smokers (subjects using nicotine containing products within 1 year of start of study should not be included).
- 10. Written informed consent given for the participation in the study.

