- Reproductive Risks: Animal studies have revealed malformations due to azathioprine. In embryo-toxicity studies, azathioprine showed teratogenic (affecting the development) or lethal effects on embryos in various animal species. In humans, however, there are contradictory findings about the teratogenic potential of azathioprine. There have been reports of intrauterine growth retardation, prematurity and low birth weight over azathioprine, especially in combination with corticosteroids. There are also reports of spontaneous abortions after both maternal and paternal exposure. Therefore, the following risk mitigation strategies have been put into place:
  - Male and female subjects at reproductive age should use a condom plus one highly effective contraceptive measures during the administration of azathioprine and at least 6 months after the end of treatment.
  - Subjects who plan to procreate within 6 months after IMP administration will not be included in the study.

- Male subjects must not have unprotected sexual intercourse with a female who is pregnant or breastfeeding during the study and for 6 months after their final dose.
- Male subjects will be instructed not to donate sperm until 6 months after the last dose.
- Females who are currently pregnant will be excluded
- Females of child bearing potential will have a pregnancy test carried out at screening, at each admission to the clinic prior to dosing and at the follow up visit.
- Should any pregnancies occur (for a female subject or female partner of a male subject, they must be reported immediately and should be followed up to determine outcome, including spontaneous or voluntary termination, details of the birth, and the presence or absence of any birth defects, congenital abnormalities, or maternal and/or new-born complications. Pregnancy outcomes must be collected for all female volunteers and the female partners of any males who took the IMP. Consent to report information regarding these pregnancy outcomes would be obtained from the mother.
- In addition to the above, to prevent exposure of any partner (male or female) a condom must be used throughout the study and for 6 months after the final dose of study drug.

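### Inclusion criterion 4 asks men for two highly effective contraceptive methods and names no condom, while the section it cites and section 5 ask for a condom plus one; the passages must be reconciled.

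*Protocol*

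**What the plan says.** The protocol sets a contraception requirement in three places.

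- **Section 7.3.1, criterion 4 (men).** The entry condition is "Male subject willing to use 2 highly effective methods of contraception from first dose until 6 months after last dose of IMP". No condom is named, and the reader is referred to section 7.2.7.3 for details.
- **Section 7.2.7.3, the section that criterion 4 cites.** Here "male subjects and their female partner must use a condom plus 1 highly effective form of contraception". Most of the listed options are then written as a condom together with a named method.
- **Section 5, Risk/Benefit Analysis, under reproductive risks.** "Male and female subjects at reproductive age should use a condom plus one highly effective contraceptive measures".

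Criterion 2 in section 7.3.1, for women of child-bearing potential, uses the condom-plus-one form: "willing to use a condom plus 1 highly effective method of contraception from first dose until 6 months after last dose of IMP".

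Sections 5 and 7.2.7.3 also carry a stand-alone condom rule. In section 7.2.7.3 it reads: "To prevent exposure of any partner (male or female) a condom must be used throughout the study", and it continues for 6 months after the final dose.

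**The concern.** Criterion 4 differs from the section it relies on, in both the number and the type of methods. Under section 7.2.1 the inclusion criteria determine who is eligible, so this wording bears on each male screening decision and on what later counts as an eligibility deviation.

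The contraception rules are also more than administrative. Section 5 describes malformations in animal studies and reports of pregnancy loss after exposure of either parent, and it presents these rules as the mitigation. The subjects are healthy volunteers with no direct benefit. An entry criterion that does not match the mitigation text leaves site staff to choose which passage to apply.

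**Working it through.** No arithmetic applies. The check sets the statements side by side and asks which men satisfy which.

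**Step 1: what each statement counts.**

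| Place | Who | Condom named? | Highly effective methods |
|---|---|---|---|
| 7.3.1, criterion 4 | men | no | 2 |
| 7.2.7.3, lead sentence | women of child-bearing potential; men and their female partners | yes | 1 |
| 5, Risk/Benefit Analysis | both sexes, reproductive age | yes | 1 |
| 7.3.1, criterion 2 | women of child-bearing potential | yes | 1 |
| 5 and 7.2.7.3, partner-exposure rule | all subjects | yes | not addressed |

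Four statements give a number of methods. Three agree with each other, and criterion 4 is the one that differs. The duration is not in dispute: where criterion 4 and the other statements give one, it is 6 months after the last dose.

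**Step 2: can the two forms mean the same thing?** Not on the protocol's own usage. Wherever it states the condom-plus-one form, it counts the condom separately from the highly effective method. A condom plus one is therefore one highly effective method with a condom, not two highly effective methods. Criteria 2 and 4 sit in the same list and are worded differently, so a reader could take the difference as intended.

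**Step 3: apply the statements literally to three men.**

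| The man is willing to use | Criterion 4 | 7.2.7.3 lead sentence and section 5 | Separate condom rule |
|---|---|---|---|
| a condom plus one highly effective method | not met | met | met |
| two highly effective methods, no condom | met | not met | not met |
| a condom plus two highly effective methods | met | met | met |

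The first row is a man who could be turned away although he meets the section that criterion 4 cites. The second is a man who could be let in without agreeing to the condom required elsewhere. The third shows that the rules can be met together.

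**Step 4: does the cross-reference settle it?** No. It takes the reader to a section that states a different rule, and nothing says which of the two prevails.

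**Step 5: a smaller point of clarity in section 7.2.7.3.** Two listed options lack the condom prefix. One begins "Vasectomised partner, provided that partner is the sole sexual partner of the female trial subject"; it is worded for female subjects and so says nothing about criterion 4. The other begins "True abstinence, only if defined as refraining from heterosexual intercourse during the entire period of risk". Both still sit under the condom-plus-one lead sentence and beside the stand-alone condom rule. The text does not say outright whether a condom is required with them.

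**The case against.** The strongest reply is that this is a drafting slip with little practical consequence. Criterion 4 points to section 7.2.7.3, which covers men expressly. Staff who follow the reference will find both the condom-plus-one rule and the separate condom rule, and may simply apply them. Criterion 4 tests willingness at entry and is not the whole conduct rule. A condom plus two highly effective methods satisfies every passage.

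Much of this stands, and it limits the point in three ways.

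- A reader might infer that the partner-exposure safeguard is lost. The documents do not support that. The condom rule in sections 5 and 7.2.7.3 is independent and unconditional, and criterion 4 neither cancels nor qualifies it. A man admitted on two methods without a condom would still be bound by it during the study.
- A reader might infer that wrong screening decisions will follow. The text shows only that they could. A literal rejection needs a man willing to use a condom plus one highly effective method but not two.
- A reader might infer that criterion 4 is the passage in error because it stands alone. Agreement among the others suggests a slip but does not establish which rule was intended, and that is a clinical decision.

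What subjects are told also cannot be judged. Section 7.2.7.3 says that contraception advice will be in the consent form, which was not among the material reviewed.

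The reply does not remove the mismatch itself. The cross-reference leads to a different rule, and an eligibility criterion should not depend on staff noticing that and choosing between them.

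**Conclusion.** The contradiction is real and lies in operative text. Criterion 4 does not match section 7.2.7.3 or section 5 on the number and type of methods, or on whether a condom is named. The result is a mismatch at entry: a man who meets section 7.2.7.3 could be excluded, and a man could qualify without having agreed to a condom.

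On size, the criterion applies to every man screened, but that describes its reach and not the number misclassified. The male share of the 30 subjects to be randomised is not stated, nor is the mix of contraceptive methods among likely volunteers, so no count or range can be given. The consequences are confined to eligibility decisions, deviation classification and the clarity of the reproductive-risk mitigation. The bioequivalence analysis and the sample size are unaffected.

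The conclusion rests on a literal reading of criterion 4 and on the protocol's own practice of counting the condom apart from the highly effective method. It should be corrected because the rule is safety-relevant and the correction is simple.

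**What to change.** Reconcile section 7.3.1 criterion 4, section 7.2.7.3 and the reproductive-risk text in section 5 so that all three give the same requirement for male subjects: the number of methods, their type, and whether a condom is required in every case. The last item should also settle the section 7.2.7.3 options that lack the condom prefix. Which requirement applies is for the sponsor's and investigator's physicians; this review does not choose between them. Bring the subject information into line where needed.

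The cost is a short change of wording, with the written approvals that section 3.1 attaches to any protocol amendment. Nothing in the SAP changes.
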